### 12.3 Treatment Groups

One (1) Treatment group. All participants will receive the same treatment (long-term DBS in PAG/PVG) and undergo the same procedural protocol. Ethical considerations forbid a control group that receives implant surgery without stimulation. Hence participants must serve as their own controls.

After internalization of the pulse generator (electronic stimulator) and subcutaneous tunneling of connecting cables to the electrode and 12-48 hours for recovery from this internalization procedure, stimulation will be applied to the patient. The patient will be asked to report their ongoing pain level, on a 0-10 numerical rating scale (NRS) with the stimulation turned off and, for each electrode contact, in small voltage steps up to the threshold for any aversive effects (if not seen in the first step). Floating, dizzy or warm feelings can be expected, based on literature reports. If there is no ongoing pain, cutaneous brushing to cause allodynia below the injury, at sensitive sites determined in the pre-surgical testing sessions, will be used. Blood pressure will also be measured by cuff before and during electrical stimulation. This will be repeated on week 12. The optimal level will be 67% of threshold for aversive or other unwanted effects (e.g. motor) or device maximum (10 V) if such effects are not observed. We expect the optimal voltage to be 4-10V. A frequency range of 10-20 Hz and pulse width range of 250-450  $\mu$ s is anticipated, but these parameters will be set according to the subject's responses. The subject returns home with the optimal stimulation settings after each programming session.

Subjects will receive monthly adjustment of stimulation levels to optimize analgesia on the NRS. They will be given the option of remaining in the study if any level becomes unpleasant in later months.

The subject will be given up to 4 different program groups after study week 16, differing in contacts, voltages, frequencies and pulse widths, all determined to be without adverse effect by the clinician programmer in the in-person office session. The subject is asked to switch program groups using their patient programmer. They switch immediately if relief is unsatisfactory, and stay with the best program for pain relief, or with any adequate program if the best is not determined, keeping a pain diary (score 0-10) at intervals of 24 hours or less to help determine the best program group.

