In addition to the continual monitoring of adverse events, safety analyses will use generalized linear models. The main dependent variable of interest is the Numeric Rating Scale (NRS) score for pain. Additionally there will be a fairly large number of dependent variables derived from assessments of other symptoms. Distributions will be modeled as binomial (yes=1 or no=0) or multinomial (e.g., score =1, 2, or 0) or normal (e.g., heart rate peak power after tilt, quantitative sensory thresholds). Less frequently, a Poisson distribution will be appropriate (e.g., number of times the patient reports autonomic dysreflexia in a given period). An appropriate link function will be chosen for each assumed distribution. Covariates to be considered are injury level, injury completeness and electrode configuration. The hypotheses to be tested for any variable (using the above factor coding) is that  $B \succ A$ ,  $C \succ B$ ,  $D \succ B$  and  $D \succ C$ . Marginal means can be used for this (except in multinomial examples, when main effects must suffice). Some participants may lack data from one condition (if they immediately opted for continuous high-level stimulation after the initial untreated period). If the continuous treatment is stopped soon after it starts, only the placebo effect ( $A \succ B$ ) will be available. Representative independent variables from each type of symptom will be further explored by discriminant analysis, which can confirm that one or more treatment condition represents a distinct state in the multivariate outcome space.

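### Section 17.1 plans contrasts among conditions A to D that the protocol never codes, and Section 17.3 claims power for tests while proposing only descriptive analysis

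*Combined protocol and SAP*

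**What the plan says.** After Table 3, Section 17.1 sets out generalized linear models with NRS pain as the main dependent variable and a fairly large set of other variables. It continues: "The hypotheses to be tested for any variable (using the above factor coding) is that", and then pairs B with A, C with B, D with B and D with C. Three further statements depend on the same conditions:

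- On gaps in the data: "Some participants may lack data from one condition (if they immediately opted for continuous high-level stimulation after the initial untreated period". This presupposes a scheme with several stimulation levels.
- On early stopping of stimulation, the plan expects to be left with the A–B pair alone, which it equates with a placebo effect.
- A discriminant analysis is planned, "which can confirm that one or more treatment condition represents a distinct state in the multivariate outcome space".

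The design sections describe one arm. Section 12.3 says "All participants will receive the same treatment (long-term DBS in PAG/PVG) and undergo the same procedural protocol", with monthly individual adjustment of settings. Section 12.5 says there is no randomization and one pattern for everyone.

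On the status of testing, Section 17.1 also calls the safety analyses mainly descriptive and says safety is not primarily a statistical evaluation. Section 17.2 calls the efficacy analysis descriptive. Section 17.3 says that nothing beyond descriptive analysis is proposed and that a formal power analysis is unwarranted. It then concludes that n=12 should give sufficient power for many of the planned tests. Its support is a published figure: a 10-point ASIA motor-score change reaches the 0.05 level with about 8 chronic patients graded ASIA A or B.

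**The concern.** The contrasts are the only formal hypotheses stated for the outcome variables, and they point back to a coding that is not there. An analyst cannot tell which time windows or stimulator states form A, B, C and D. If the gap were left open until the data were in, the conditions would be chosen with open-label results in view, for NRS pain and for every other variable modelled.

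Section 17.3 adds to this. Its power sentence invites a reader to treat those tests as adequately powered, but the argument concerns another outcome (ASIA motor score) in a narrower group (ASIA A or B). The main variable is NRS pain, and Section 13.3 admits ASIA A to D.

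**Working it through.** **1. Is there a coding anywhere?** Each place that could supply A to D:

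| Place | What it offers | Could it be the coding? |
|---|---|---|
| Section 17.1, text before the sentence | Descriptive aims, Table 3, model families, covariates | No condition is named |
| Section 12.3, titration | Ratings with stimulation off, then "for each electrode contact, in small voltage steps up to the threshold for any aversive effects"; repeated at week 12 | No: individual thresholds, no labels |
| Section 12.3, programs | "The subject will be given up to 4 different program groups after study week 16", with the participant "keeping a pain diary (score 0-10) at intervals of 24 hours or less" | No: an individual number and content of programs, all active stimulation, so none can be the untreated period |
| Sections 12.3 and 14.3.4, cycling | On/off cycling if sleep is affected or continuous stimulation is not tolerated | No: conditional |
| Section 12.5 and Table 2 | Stimulator inactivated at programming sessions (possibly 5 minutes), used to look at placebo effects | An off state, but unlabelled |
| Section 12.7 D | Constant stimulation at the best amplitude, or none | No: optional for individuals |
| Section 12.6.1, extension | Two to four home settings carrying the letters A to D | No: individually chosen settings in weeks 53 to 156, whereas 17.1 starts from an initial untreated period |

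The passages removed from the public copy do not explain the gap, since Section 17 is present from 17.1 to 17.5.

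**2. How many levels can be recovered?** Pre-implant baseline, stimulator-off and stimulator-on give two or three levels. No fourth condition is common to all 12 participants. The off state is also thin. Table 2, note 1, places the listed pain, depression, cognitive and sensory assessments before stimulator adjustment, so the schedule does not supply off-state values for most of the variables to which the contrasts are meant to apply.

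**3. The plan's own figure.** The n of about 8 cannot be reproduced from the documents. SD, power, sidedness and design are not given there (they may be in the cited source), and any number of SDs would fit. It would not carry over to NRS pain in any case.

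**4. What n=12 gives for a paired change.** Inputs: n=12 (Synopsis; Section 12.2); two-sided alpha 0.05; paired t. Ten completers is an assumption.

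Half-width of the 95% CI, in SDs of the within-subject change = t(n−1, 0.975)/√n:

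- n=12: 2.201/3.464 = 0.635
- n=10: 2.262/3.162 = 0.715

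The smallest change with 80% power is the d that solves 1 − F(t(n−1, 0.975); n−1, d√n) = 0.80, where F is the noncentral t distribution function:

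- n=12: d = 0.889 (d√n = 3.08)
- n=10: d = 0.996 (d√n = 3.15)

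The documents give no SD for NRS change. For a range of assumed values at n=12:

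| Assumed SD of change (NRS points) | CI half-width | Change with 80% power |
|---|---|---|
| 1.5 | 0.95 | 1.33 |
| 2.0 | 1.27 | 1.78 |
| 2.5 | 1.59 | 2.22 |

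**5. Which pain score, and when?** Table 2 has no row named NRS. Section 17.1 refers both to an NRS score and to a Pain Assessment Scale score that matches no scheduled instrument. The ISCI/NPSI row has 25 assessments: weeks 2, 4 and 6 (3), then even weeks 10 to 52 ((52−10)/2 + 1 = 22). The time of the main analysis is also unsettled. The Synopsis (concomitant medication) and Section 13.3 call 12 weeks after surgery the primary endpoint, while the Synopsis (primary safety analysis) puts the primary endpoint analyses at 44 weeks post-implantation, the time point that Section 17.1 also uses.

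**The case against.** The strongest reply is that this is a 12-person Phase 1 study. Sections 17.1, 17.2 and 17.3 all lean on description, so the contrasts are subsidiary. That stands, and it limits the seriousness: the descriptive pain analyses can proceed without the A–D text.

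A second reply is that the conditions can be guessed. Section 17.1 mentions an untreated period and a placebo effect, and Section 12.5 plans to examine placebo effects with the stimulator off. This stands in part. A reader might infer that the design has no conditions to compare at all. The documents do not support that, because baseline, off and on states are there. What is missing is the mapping, the time windows and a fourth level.

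A third is that the letters do appear in the extension. They do, but for individual home settings after week 52.

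A reader might also infer that the analyst is bound to invent conditions after seeing the data. That does not follow either, since an amendment before analysis could define them. Nor does the weak support for the power sentence show that 12 is too few for a Phase 1 study. It shows only that nothing in the plan supports the claim for pain.

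**Conclusion.** The point holds in this form. The four contrasts in Section 17.1 and the discriminant analysis of treatment conditions cannot be run as written: the coding they cite is absent, and the one-group design supplies at most two or three unlabelled states. Section 17.3 contradicts itself and Section 17.1 on whether tests are planned, and its power argument uses a different outcome in a narrower population.

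All four contrasts are affected. For one paired comparison, n=12 gives a half-width of 0.64 SD and 80% power only from 0.89 SD upwards; with 10 completers (assumed) these are 0.72 and 1.00 SD. The figures rest on a paired t analysis, roughly normal changes and observed pairs. The values in NRS points rest on assumed SDs.

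This should be corrected, but it does not undermine the descriptive analyses.

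**What to change.** 1. **Section 17.1, contrasts.** Delete the A–D contrasts and the sentences that depend on them (data missing from one condition, placebo effect only, discriminant analysis of conditions). Alternatively, by amendment before analysis, replace them with states the design does supply (pre-implant baseline, stimulator-off at programming sessions, stimulator-on), each with its time window. Keep the time-series analysis of Section 12.5 and the correlations with amplitude adjustment of Section 15 as descriptive.

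2. **One pain contrast.** Name a single within-subject NRS change from the protocol's week-2 baseline (Table 1; Section 14.3.1) to one scheduled on-stimulation time point. First reconcile the 12-week and 44-week endpoint statements. State which Table 2 instrument supplies the NRS. Report the mean paired change with a t-based 95% CI, say whether it uses observed pairs or values imputed under Section 17.4, and label all other variables descriptive.

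3. **Section 17.3.** Replace the power sentence with: *With 12 participants the 95% CI half-width for a paired change is 0.64 SD of the within-subject change, and 80% power (two-sided 0.05, paired t) is reached only for 0.89 SD or more; if 10 complete (assumed), 0.72 and 1.00 SD.*

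Cost: text edits to Sections 17.1 and 17.3 and to the endpoint wording in the Synopsis and Section 13.3. No visits are added if the ISCI/NPSI row supplies the score. The downside is fewer nominal tests and a less favourable statement than the present power claim.

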## 17 STATISTICAL CONSIDERATIONS

### 17.1 Safety Analyses:

The analyses for safety will be mainly descriptive, focusing on trends for within-subject differences and changes in reported pain intensity during routine patient visits for the duration of the study. The expected outcome is stable, long-lasting change in the Pain Assessment Scale score from baseline to 44 weeks post-implant .All AEs and SAEs will be listed and their incidence compared to historical controls. The primary safety analysis will be conducted on all patient data when all 12 participants have completed the study.

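### The discriminant analysis in 12 repeatedly measured participants is said to confirm a distinct treatment state, with no criterion, no validation and no handling of the pairing

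*Combined protocol and SAP*

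**What the plan says.** Section 17.1 (the paragraph on generalized linear models after Table 3) ends with a multivariate step: "Representative independent variables from each type of symptom will be further explored by discriminant analysis". The same sentence then claims more for the method than exploration, namely that it is one "which can confirm that one or more treatment condition represents a distinct state in the multivariate outcome space". A single sentence thus calls the analysis exploratory and credits it with confirmation.

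The sample is 12 people in one group: "The primary safety analysis will be conducted on all patient data when all 12 participants have completed the study". Section 12.3 makes the comparison within person: "Hence participants must serve as their own controls".

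The conditions to be separated appear as letters A to D, "using the above factor coding", but no such coding appears in the supplied text. Section 17.1 also expects gaps: "Some participants may lack data from one condition".

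The plan does not name the variables to be entered, their number, the rule for choosing them, the rows contributed by each participant, any cross-validation or permutation, or what would count as distinct.

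**The concern.** Linear discriminant analysis picks the combination of variables that best separates the groups in the data at hand. Scored on those same data, it separates groups that do not differ, and the excess over chance grows with the number of variables relative to the number of rows. With 12 participants that excess is not negligible even for a handful of variables. A reader who takes good in-sample separation as the promised confirmation could report a multivariate treatment state that is only fitting error.

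The study is open label and uncontrolled (Section 12.5). Its purpose is to judge whether a larger study is warranted (Synopsis, Study Rationale). A claim that stimulation produces a distinct state would carry weight in that judgement, so the plan should say what evidence would support it.

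**Working it through.** The plan gives no figure for this analysis, so there is none to reproduce. The check asks how much separation appears when no condition differs from any other.

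**Inputs from the documents.** 12 participants (Section 17.1); within-person comparison (Section 12.3); four condition labels (Section 17.1).

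**Assumptions, because the documents are silent.**
- Number of conditions compared, K: 2 or 4.
- One row per participant per condition, so 12 × 2 = 24 or 12 × 4 = 48 rows.
- Number of variables, p: 3 to 15. Section 16 groups the assessments into four domains (motor and sensory, pain, autonomic, quality of life), so p = 4 is one variable per domain.
- Within-participant correlation, ρ: 0.5, with 0 as a sensitivity.

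**Method.** Gaussian noise with no condition effect, 400 simulated trials per setting. Each row x is assigned to the condition k with the smallest (x − m_k)′S⁻¹(x − m_k), where m_k is the condition mean and S the pooled within-condition covariance. In-sample accuracy is rows correctly assigned ÷ all rows. Leave-one-participant-out (LOPO) accuracy refits without a participant and then classifies that participant's rows. Wilks' test uses Bartlett's chi-square at 5% and treats rows as independent.

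**Results, 12 participants, ρ = 0.5, pure noise.**

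| p | K=2 in-sample | K=2 LOPO | K=2 Wilks rejects | K=4 in-sample | K=4 LOPO | K=4 Wilks rejects |
|---|---|---|---|---|---|---|
| 3 | 60.0% | 50.6% | 0.75% | 34.9% | 25.1% | 0.25% |
| 4 | 62.2% | 49.6% | 1.0% | 36.8% | 24.9% | 0% |
| 8 | 70.0% | 50.2% | 0.5% | 44.9% | 25.2% | 0% |
| 10 | 74.3% | 49.6% | 1.5% | 48.5% | 25.6% | 0% |
| 15 | 85.7% | 50.0% | 2.75% | 57.5% | 24.9% | 0% |

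Chance is 50% for two conditions and 25% for four. A separate simulation of the p = 4 case gave about 63% and 37%.

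**Sensitivity.**
- Independent rows (ρ = 0) give more in-sample separation. Two conditions: 63% at p = 3, 67% at p = 4, 91% at p = 15. Four conditions: 39%, 41% and 66%.
- Ten participants per condition, p = 10, ρ = 0.5: 78.5% against 74.3% for two conditions, and 51.9% against 48.5% for four.
- Three rows per participant per condition, two conditions: 57–59% at p = 4 and 60–63% at p = 8. The excess shrinks but remains.

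**Why the Wilks' test becomes conservative.** With unit variance, the spread of rows within a condition is ρ + (1 − ρ) = 1, which includes the differences between people. The difference between two condition means has variance 2(1 − ρ)/12, because each person appears in both conditions. At ρ = 0.5 this is 2 × 0.5/12 = 0.083, whereas a test that ignores pairing expects 2/12 = 0.167. The test measures differences against noise twice too large and rejects far below 5%. With independent rows its level is roughly right for small p: 4–7% with four conditions, and 3–6% with two conditions up to p = 10. With two conditions it then rises to about 10% at p = 15 and 32% at p = 20.

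**The case against.** The strongest reply is that the plan never says distinctness will be judged by in-sample accuracy. A reader might infer that following Section 17.1 would necessarily produce a false treatment effect. The documents do not support that, since they name no criterion. An analyst using the ordinary Wilks' test with few variables would not call noise distinct. This part of the reply stands. It does not rescue the claim of confirmation, because that test ignores the pairing and at ρ = 0.5 rejects almost never, so it is not a sound reference either.

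A reader might also infer that the number of variables approaches the number of people, because Section 17.1 says "there will be a fairly large number of dependent variables derived from assessments of other symptoms". That sentence describes outcomes for the generalized linear models. The discriminant analysis takes only representative variables from each symptom type, which could be as few as four. The upper end of the range is therefore possible but not stated.

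Finally, Section 17.1 calls the safety analyses mainly descriptive, Section 17.3 proposes nothing beyond description, and no endpoint or stopping rule depends on this step. That limits the consequence. It does not reconcile exploring with confirming in one sentence.

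**Conclusion.** The point holds in a limited form. The plan attributes confirmation to an analysis that has no stated criterion, no validation and no handling of repeated measures.

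If separation is read in-sample, noise alone gives about 60–86% apparent accuracy for two conditions and 35–58% for four over p = 3 to 15, and about 62–63% and 37% at p = 4. These figures assume Gaussian data, one row per participant per condition and ρ = 0.5. They would be larger with independent rows or fewer participants, and smaller with more rows per person. At p = 1 the excess is small: 54.7% for two conditions and 29.6% for four.

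The documents do not show that the method is bound to find an effect, nor that discriminant analysis is unusable here. This is a secondary analysis, and the change is a cheap improvement rather than a repair to the main results.

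**What to change.** In Section 17.1:

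1. Replace *can confirm* with *will explore*.
2. Define conditions A to D and state which rows each participant contributes to each. The remaining steps cannot be carried out until this is done.
3. Pre-name a short variable list, for example one per Section 16 domain.
4. Report leave-one-participant-out accuracy, not in-sample accuracy, and compare it with its distribution when condition labels are permuted within participant. With two conditions and 12 complete participants there are 2¹² = 4,096 relabellings, enough for a usable reference. Participants lacking a condition are permuted over the conditions they have.

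The alternative is to drop the discriminant analysis.

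Holding out whole participants removes the in-sample optimism, and permuting within participant respects the pairing. Even then, a positive result would show that the conditions differ, not that stimulation is the cause, because the untreated period comes first.

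The cost is a few lines of text, a little programming and a weaker claim. No new data are needed.

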**17.2 Efficacy Analyses:**

To test the core hypothesis and secondary outcome measures, the analysis (descriptive) for efficacy trends will be conducted on the baseline through 52 weeks of data collection for all twelve (12) participants enrolled.

The one-minute recordings of local fields potentials from the bilateral or unilateral contacts PAG/PVG by the PC+S device will be analyzed in the time domain (autocorrelations and inter-lead cross-correlations) and the frequency domain (power in alpha, beta, gamma and delta EEG bands). Peaks in spectra or in auto- or cross-correlations will be examined for correlations with pain level (analgesia obtained) for each contact or pair of contacts. The potential ability shown by these results for usefulness in electrode targeting of future subjects (with pain from SCI or other causes) will be evaluated. That is, their

predictions of efficacy will be evaluated. These preliminary findings will be considered in the planning of studies with larger subject populations with pain of adequate statistical power.

